1. OBJECTIVES

Disclosing Recovery: A Decision Aid and Toolkit is a patient decision aid that was developed to help people in treatment for OUD make key decisions regarding disclosure and build skills to disclose.

- Primary aims of the current pilot randomized controlled trial are to examine the implementation of the intervention to inform a future efficacy trial. More specifically, participants' perceptions of the intervention's acceptability and feasibility will be assessed. Additionally, the intervention's impact on decision-making quality will be assessed.
- Secondary aims are to explore the intervention's impact on relationship characteristics, including social support and enacted stigma, and commitment to sobriety.

2. DESIGN

This is a pilot, parallel randomized controlled trial. Data will be collected from participants at two time points, spaced one month apart, by a research assistant. All participants will be recruited from the waiting room at Brandywine Counseling & Community Services. The research assistant will **screen** interested individuals for eligibility in person (recruitment strategy described below) and schedule study appointments, which may be coordinated with treatment appointments. All study screening and appointments will be conducted in private spaces (i.e., otherwise empty conference room and/or offices) at Brandywine Counseling & Community Services. Participants will receive \$50 gift certificates for completing each time point, and a \$10 bonus gift card for completing both time points within 1 week of when it was scheduled.

At the **first study appointment**, the research assistant will introduce the study, check for questions, and obtain consent for the study procedures, and follow up procedures. Participants will be assured that study data will be kept confidential (including from clinic staff). Participants will be randomly assigned to receive either the disclosure intervention (n=25) or a control intervention (i.e., an evidence-based mindfulness intervention, n=25).

- Disclosure Condition: Participants will be guided through a workbook and accompanying worksheet designed to help them: (1) decide whether or not they want to share information about their substance use with others, and (2) build skills for disclosing (e.g., planning what to say). Importantly, the intervention is not designed to encourage participants to disclose or not disclose (please see intervention booklet included with this protocol submission), but rather to help participants decide whether they want to disclose based on their own goals and values. Our intervention is an adaptation of a previously published disclosure intervention (i.e., the CORAL), which is associated with reduced decisional conflict surrounding disclosure and greater job retention (Henderson et al., 2013).
- Control Condition: Participants will be able to choose from several guided meditations offered by Headspace. Headspace offers a series of introductory videos on mindfulness. Evidence suggests that usage of the Headspace app over time is associated with decreases in perceived stress and increases in general well-being (Flett et al., 2019; Mani et al., 2015; Yang et al., 2018). Although the videos have yet to be evaluated in terms of their effects on stress and well-being, they review the same content as the app in a more interactive format and therefore may yield similar effects.

Along with completing the disclosure or control condition activity, participants will be asked to respond to several survey and interview questions to gauge the acceptability, feasibility, and

preliminary efficacy of the intervention materials. The first appointment is expected to last less than one hour.

At the **second study appointment**, participants will again be asked to respond to survey and interview questions designed to further evaluate the acceptability, feasibility, and preliminary efficacy of the intervention. The second appointment is expected to last up to 30 minutes. In particular, we will investigate whether participants who completed our disclosure intervention report better disclosure experiences than participants who completed the control condition. Participants will be able to complete the second study appointment by phone or in person at Brandywine Counseling & Community Services.

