3. METHODS

We aim to recruit 50 adults receiving SUD treatment. People in recovery will be eligible if they are:

- 18 years or older;
- currently receiving outpatient treatment at Brandywine Counseling & Community Services;
- are considering disclosing their SUD recovery status to at least one person in the next month;
- have access to a phone that can receive text messages and phone calls;
- and have no current diagnosis of severe mental illness.

Participants will be recruited from Brandywine Counseling and Community Services. Brandywine Counseling and Community Services serves approximately 3,000 clients per year. The study will be advertised via recruitment flyers that will be available in waiting rooms and distributed to clients. Participants will be instructed to contact a research assistant, who will be available in waiting rooms, if they are interested in participating in the study. Participants will also have the opportunity to email or call the study team to express interest in the study. Individuals who indicate interest in the study will be asked to fill out an electronic screener in a private room. After answering several questions on an iPad, individuals will be notified whether or not they are eligible to participate. The research assistant will not have access to individuals' individual answers – they will only be able to access information regarding whether individuals are eligible or not.

When eligible individuals sign up for the study, we will ask for permission to send them a reminder text the day before their scheduled appointment. A reminder text will only be sent to participants who agree to be contacted.

People with self-reported bipolar I disorder and schizophrenia will not be eligible to participate in the sample of people in recovery given that relational processes for these individuals may not generalize to others in recovery from SUDs. People with mood and anxiety disorders will be eligible.

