4. STATISTICAL ANALYSIS PLAN

Participant characteristics will be explored using descriptive statistics. Primary and secondary outcomes will be evaluated with t-test and chi-square tests comparing participants in the *Disclosing Recovery* versus comparator conditions. Because opioid use is hypothesized to impact interpersonal interactions, we will additionally explore whether baseline opioid use moderates associations between intervention assignment with relationship outcomes with two-

way analyses of variance (ANOVA). Statistically significant associations will be further explored. Primary analyses will include the full sample of participants, and secondary analyses will include the full sample of participants for preliminary efficacy analyses or participants who completed the second appointment only for relationship outcome analyses.

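### Opioid use is the plan's only named moderator, but no stratification on it is described and no adjustment for it is stated; stratifying would be a cheap, modest improvement

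*Combined protocol and SAP*

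**What the plan says.** On allocation, Section 2 (Design) states: "Participants will be randomly assigned to receive either the disclosure intervention (n=25) or a control intervention", also with 25. Section 3 (Methods) gives the total: "We aim to recruit 50 adults receiving SUD treatment". Neither section describes how the sequence is generated, or any blocking, stratification, minimisation or concealment.

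Entry depends on "currently receiving outpatient treatment at Brandywine Counseling & Community Services" and other criteria, none of which is opioid use. So opioid use can vary between participants.

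Section 4 (Statistical Analysis Plan) gives opioid use a special role. Its rationale begins "Because opioid use is hypothesized to impact interpersonal interactions", and it continues: "we will additionally explore whether baseline opioid use moderates associations between intervention assignment with relationship outcomes", using two-way ANOVA. No other moderator is named. The coding of opioid use and its expected frequency are not given.

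For the arm comparisons, Section 4 says "Primary and secondary outcomes will be evaluated with t-test and chi-square tests". No covariate is mentioned. Relationship outcomes are a secondary aim in Section 1, and Section 4 analyses them only in participants who complete the second appointment.

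**The concern.** The plan singles out one patient characteristic as likely to affect the relationship outcomes, and then describes no protection for it at allocation or in the arm comparisons. Two things follow in a trial of 50.

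- Chance can place noticeably more opioid users in one arm. An unadjusted comparison of social support or enacted stigma then carries part of the opioid-use effect.
- The arm by opioid-use analysis depends on four cells. If users are few, an uneven split followed by dropout can leave one cell with only a handful of people.

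Both are easy to reduce at the design stage and cannot be undone by design afterwards. The pilot is meant to inform an efficacy trial, so trying the procedure now also has some value of its own.

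**Working it through.** **The plan's own figure.** 25 + 25 = 50, which agrees between Sections 2 and 3. No alpha, power, effect size, SD or dropout rate is given, so there is no sample-size calculation to reproduce.

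**Assumptions.** Opioid use is yes/no; prevalence is 20%, 30%, 40% or 50% (K = 10, 15, 20 or 25 users of 50); 80% return for the second appointment, independently of arm and opioid use. Prevalences above 50% mirror these, with non-users as the scarce group.

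**1. Imbalance between arms.** Under unstratified 25:25 allocation, the number of users X in one arm is hypergeometric (50, K, 25). The arms differ by |2X − K|/25, so 20 points or more means |2X − K| ≥ 5, and 28 points or more means |2X − K| ≥ 7.

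| Prevalence (K) | P(≥ 20 points) | P(≥ 28 points) | P(an arm has 0 or 1 users) |
|---|---|---|---|
| 20% (10) | 7.4% | 1.1% | 1.1% |
| 30% (15) | 21.7% | 6.2% | 0.01% |
| 40% (20) | 14.8% | 4.2% | about 0 |
| 50% (25) | 25.8% | 8.9% | about 0 |

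The first column is not monotone because, when K is even, the smallest qualifying difference is 6 users (24 points) rather than 5.

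**2. What an imbalance does to an unadjusted comparison.** Shift = imbalance × opioid effect. With an assumed effect of 0.5 to 0.8 SD, a 20-point imbalance gives 0.20 × 0.5 = 0.10 SD to 0.20 × 0.8 = 0.16 SD. A 28-point imbalance gives 0.14 to 0.22 SD.

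**3. Thin user cells at the second appointment.** Given x users in one arm, the chance that either user cell ends at 2 or fewer is 1 − [1 − P(Bin(x, 0.8) ≤ 2)] × [1 − P(Bin(K − x, 0.8) ≤ 2)]. For the unstratified figure this is averaged over X. For the stratified figure the split is taken as even, or within one when K is odd. At K = 10 and 5:5, P(Bin(5, 0.8) ≤ 2) = 0.058, so 1 − (1 − 0.058)² = 0.11.

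| Prevalence | Unstratified | Stratified |
|---|---|---|
| 20% | 29.5% | 11.2% |
| 30% | 3.3% | 0.6% |
| 40% | 0.2% | 0.02% |
| 50% | 0.01% | < 0.001% |

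**4. Precision of the interaction.** The variance is proportional to the sum of 1/(cell size). Averaged over X and divided by the value for the most even split, the ratio is 1.09, 1.04, 1.03 and 1.02 at 20%, 30%, 40% and 50%. (At 20% this leaves out splits with an empty cell, probability 0.06%.) A bad split costs more when users are few. At 20% prevalence, 8:2 gives 1/8 + 1/17 + 1/2 + 1/23 = 0.727, against 1/5 + 1/20 + 1/5 + 1/20 = 0.500 for 5:5, a 45% increase.

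**5. What stratifying cannot do.** With all 50 analysed, two-sided alpha 0.05 and 80% power (both assumed), the detectable interaction is 2.80 × √(sum of 1/cell size) SD. With even splits that is 2.80 × 0.566 = 1.59 SD at 50% prevalence and 2.80 × 0.707 = 1.98 SD at 20%.

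**The case against.** The case against is substantial, and most of it stands.

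- **Silence is not a design choice.** The documents do not say that allocation is unstratified; they do not describe the method at all. The supportable statement is that stratification is not described.
- **Severe imbalance is uncommon.** A reader might infer that one arm could easily end up with almost no opioid users, or that the interaction could become inestimable. The figures do not support this: an arm with 0 or 1 users has about a 1% chance at 20% prevalence and almost none at 30% to 50%. The 20-point threshold is also a reviewer's choice.
- **The ANOVA is partly protected.** A two-way ANOVA normally includes the opioid-use main effect, so imbalance there costs precision and does not confound. The exposed analyses are the t-tests and chi-square tests, and under randomisation their chance imbalance is covered by the nominal error rate.
- **The gain is small and the stakes are low.** The average variance penalty is 2% to 9%, and N = 50 is the main limit on the moderation analysis. The analyses affected are secondary or exploratory.

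A reader might also infer that opioid use is asked after the session and so reported differently by arm. Section 2 does say "Along with completing the disclosure or control condition activity, participants will be asked to respond to several survey and interview questions", but that sentence fixes no order and concerns acceptability, feasibility and preliminary efficacy. Section 4 calls the factor baseline opioid use. Late measurement is therefore conjecture. What can be said is that its timing is not specified.

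What survives is that the plan names one influential factor, describes no use of it at allocation and states no adjustment for it, and that changing this costs little.

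**Conclusion.** The point holds as a cheap improvement of low severity. If allocation is in fact unstratified, the chance of a 20-point or larger difference in opioid use is 7% to 26% at an assumed prevalence of 20% to 50%. Stratifying matters most if users (or non-users) are about a fifth of the sample: it then cuts the chance of a user (or non-user) cell of 2 or fewer from 30% to 11%, given 80% return. At 30% to 50% prevalence that risk is about 3% or less even without stratifying, and the precision gain averages 2% to 4%.

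This is chance imbalance and lost precision, not systematic bias. It does not touch the trial's validity or its primary aims, and stratifying would not make a 50-person moderation analysis informative. The figures rest on yes/no coding, the assumed prevalence range and the assumed return rate, none of which the documents give.

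**What to change.** 1. In Section 2, state the randomisation method. Define opioid use as a yes/no factor and record it on the iPad after consent and before assignment.
2. Assign 1:1 from a concealed, automated list stratified on that answer, in randomly varied blocks. The iPad should return only the assignment, so that the research assistant does not see the answer. This keeps to the Section 3 arrangement for screener responses.
3. In Section 4, use the recorded value as the ANOVA factor. Include it also in the relationship-outcome arm comparisons, so that the analysis reflects the stratification: a model with arm and opioid use in place of the t-test, and a Mantel–Haenszel test in place of the plain chi-square.

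Cost: one question placed before assignment, a two-stratum list in place of one, and a simple automated assignment step. Arm sizes may differ from 25 by one or two. If stratified assignment is not practical, items 1 and 3 alone would still give a pre-assignment factor and prespecified adjustment, but would not reduce the thin-cell risk.

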3. METHODS

We aim to recruit 50 adults receiving SUD treatment. People in recovery will be eligible if they are:

- 18 years or older;
- currently receiving outpatient treatment at Brandywine Counseling & Community Services;
- are considering disclosing their SUD recovery status to at least one person in the next month;
- have access to a phone that can receive text messages and phone calls;
- and have no current diagnosis of severe mental illness.

Participants will be recruited from Brandywine Counseling and Community Services. Brandywine Counseling and Community Services serves approximately 3,000 clients per year. The study will be advertised via recruitment flyers that will be available in waiting rooms and distributed to clients. Participants will be instructed to contact a research assistant, who will be available in waiting rooms, if they are interested in participating in the study. Participants will also have the opportunity to email or call the study team to express interest in the study. Individuals who indicate interest in the study will be asked to fill out an electronic screener in a private room. After answering several questions on an iPad, individuals will be notified whether or not they are eligible to participate. The research assistant will not have access to individuals' individual answers – they will only be able to access information regarding whether individuals are eligible or not.

When eligible individuals sign up for the study, we will ask for permission to send them a reminder text the day before their scheduled appointment. A reminder text will only be sent to participants who agree to be contacted.

People with self-reported bipolar I disorder and schizophrenia will not be eligible to participate in the sample of people in recovery given that relational processes for these individuals may not generalize to others in recovery from SUDs. People with mood and anxiety disorders will be eligible.

4. STATISTICAL ANALYSIS PLAN

Participant characteristics will be explored using descriptive statistics. Primary and secondary outcomes will be evaluated with t-test and chi-square tests comparing participants in the *Disclosing Recovery* versus comparator conditions. Because opioid use is hypothesized to impact interpersonal interactions, we will additionally explore whether baseline opioid use moderates associations between intervention assignment with relationship outcomes with two-

way analyses of variance (ANOVA). Statistically significant associations will be further explored. Primary analyses will include the full sample of participants, and secondary analyses will include the full sample of participants for preliminary efficacy analyses or participants who completed the second appointment only for relationship outcome analyses.

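### The only statistical analysis stated for acceptability and feasibility is a test against Headspace; no Disclosing Recovery arm estimate with a confidence interval is planned as the answer to this primary aim

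*Combined protocol and SAP*

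**What the plan says.** Section 1 (Objectives) says that the primary aims "are to examine the implementation of the intervention to inform a future efficacy trial". It then makes this specific: "participants' perceptions of the intervention's acceptability and feasibility will be assessed". It adds decision-making quality as a further primary aim ("impact on decision-making quality will be assessed").

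Section 2 (Design) fixes the size and the comparator: "Participants will be randomly assigned to receive either the disclosure intervention (n=25) or a control intervention", with 25 in the control arm as well, who choose among Headspace meditations. At the first appointment participants are "asked to respond to several survey and interview questions to gauge the acceptability, feasibility" and preliminary efficacy. At the second, one month later, they answer "survey and interview questions designed to further evaluate the acceptability, feasibility, and preliminary efficacy of the intervention".

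Section 4 (Statistical Analysis Plan) gives one method for every primary and secondary outcome: "Primary and secondary outcomes will be evaluated with t-test and chi-square tests comparing participants in the" two conditions. Descriptive statistics are named for one purpose only: "Participant characteristics will be explored using descriptive statistics". No estimate within the Disclosing Recovery arm, confidence interval or benchmark is stated for acceptability or feasibility, and no method is stated for the interview answers.

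**The concern.** The aim asks how the intervention is received. The stated method asks whether it is rated differently from Headspace. A two-sample test is built on the difference between arms, so a well-rated and a poorly rated intervention can give the same result.

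At stake is what this pilot passes on. Its declared purpose is to inform a later efficacy trial, and the planner of that trial needs to know how acceptable and feasible Disclosing Recovery was, and how firmly 25 people can establish it. As written, the main result would be a difference from an active comparator, and the uncertainty of the quantity of interest would not be part of the plan.

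The concern does not extend to decision-making quality. That aim is about the intervention's effect, and a between-arm comparison is the right form for it.

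**Working it through.** **Inputs.** From the documents: 25 per arm (Section 2) and a t-test or chi-square test between arms (Section 4). The documents give no instrument, SD, rate, alpha or benchmark, so the scale, SDs, means, counts and the two-sided 5% level below are assumptions for illustration. Section 4 has no figure for these outcomes to reproduce.

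**1. Mean score, assumed 1 to 5 scale, SD 0.8 in both arms.**

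- Standard error of the difference: 0.8 × √(2/25) = 0.226.
- Means 4.3 v 3.8: t = 0.5/0.226 = 2.21 on 48 df, p = 0.032.
- Means 2.8 v 2.3: the difference is again 0.5, so t = 2.21 and p = 0.032.
- 95% CI for the Disclosing Recovery mean: mean ± t(0.975, 24) × 0.8/√25 = mean ± 0.33. This gives 3.97 to 4.63 in the first case and 2.47 to 3.13 in the second.

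The test cannot separate the two cases; the intervals do not overlap. With other SDs the p-value moves (0.005 at SD 0.6, 0.084 at SD 1.0, 0.147 at SD 1.2) but stays the same for both pairs, because a common shift cancels.

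**2. Binary outcome (Pearson chi-square without continuity correction; exact 95% CIs).**

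| Disclosing Recovery v Headspace | p | Disclosing Recovery, 95% CI |
|---|---|---|
| 23/25 v 15/25 | 0.008 | 92% (74.0% to 99.0%) |
| 10/25 v 2/25 | 0.008 | 40% (21.1% to 61.3%) |
| 22/25 v 22/25 | 1.00 | 88% (68.8% to 97.5%) |
| 10/25 v 10/25 | 1.00 | 40% (21.1% to 61.3%) |
| 20/25 v 25/25 | 0.018 | 80% (59.3% to 93.2%) |

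Rows 1 and 2 share a p-value at very different levels, and so do rows 3 and 4. In the last row the test goes against an intervention that 80% accept (p = 0.059 with continuity correction, 0.050 by Fisher's test).

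**3. What a non-significant result would say.** With 25 per arm and two-sided 5%, t-test power is about 11%, 41% and 79% for standardised differences of 0.2, 0.5 and 0.8. Failing to find a difference from Headspace would therefore say little about either arm.

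**4. Precision of the proposed estimate.**

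- Mean, n=25: half-width t(0.975, 24)/√25 = 0.41 SD.
- Mean, if only 20 respond at the second appointment (an assumed number): t(0.975, 19)/√20 = 0.47 SD.
- Proportion, n=25: exact limits lie up to about 21.5 points from the estimate. For example, 17/25 is 68% with a lower limit of 46.5%. The intervals are asymmetric: for 20/25 the limits are 20.7 points below and 13.2 above.

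**The case against.** The strongest reply is that nothing is lost. Arm means or proportions would normally be shown beside the tests, and with an SD or a count anyone can compute the interval. This largely stands, and it limits the harm. A reader might infer from Section 4 that the level of acceptability will go unknown; the documents do not support that. What remains is that Section 4 promises neither the arm estimate nor its uncertainty, and makes a different quantity the result for the aim.

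Second, the survey is not the only source. Section 2 plans interview questions on acceptability and feasibility at both appointments. A reader might conclude that these aims are assessed by a significance test and nothing else; that is too strong. The accurate statement is that the test is the only statistical analysis stated. The lack of an interview method in a short SAP does not show that the interviews will go unused.

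Third, the link from aims to outcomes is inferred, since no list of primary outcomes is given. Nor do the sections map cleanly: Section 4 places preliminary efficacy under secondary analyses, while Section 1 makes decision-making quality a primary aim. This stands as a caveat. But if acceptability and feasibility are not among the primary outcomes of Section 4, a primary aim has no stated statistical analysis unless they count as secondary outcomes, which get the same test.

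Fourth, Headspace is a useful reference. Participants are paid and a research assistant collects the answers, so absolute ratings could be inflated, and a randomised comparator rated under the same conditions helps to interpret them. This is a good reason to keep the comparison. It does not turn the comparison into an estimate of how Disclosing Recovery was received.

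**Conclusion.** The point holds in a limited form. For acceptability and feasibility, the one stated statistical method answers a different question from the primary aim, and the estimate that would answer it is not planned with its uncertainty or as the main result. This rests on reading the primary aims as the primary outcomes. That the test does not depend on a common level follows from its form for means; the particular p-values and intervals rest on assumed scales, SDs and counts, and measure nothing observed in this trial.

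The size is moderate. The trial is not invalidated, the needed data are already to be collected, and the arm levels would probably be reported. The documents do not support a claim that the between-arm tests are wrong or should go: they suit decision-making quality and are useful context for the other two outcomes. The change is worth making before analysis because the uncertainty at n=25 is large (20 of 25 is compatible with 59% to 93%) and the next trial's planners need to see it.

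**What to change.** In Section 4, add that:

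- acceptability and feasibility will each be reported as the mean or proportion in the Disclosing Recovery arm with a 95% CI, as the main result for these two outcomes, using first-appointment ratings in all participants randomised to that arm;
- second-appointment ratings will be reported in the same way among those who attend, with the number responding, because the full sample cannot supply month-1 ratings for those who miss that visit;
- the planned comparison with Headspace will be shown alongside as supportive;
- the between-arm test remains the analysis of decision-making quality.

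The cost is a few sentences, with no new data, visits or participants, and every planned test stays. The downside is that the intervals are wide, and wider at month 1 if some participants do not return. That width should be reported, since it is part of what the pilot has to tell the efficacy trial.

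### Does following up only statistically significant opioid-use interactions, in at most 50 completers, call for a change to the analysis plan?

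*Combined protocol and SAP*

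**What the plan says.** Section 4 compares the arms by t-tests and chi-square tests, then adds a moderation analysis by two-way ANOVA: "we will additionally explore whether baseline opioid use moderates associations between intervention assignment with relationship outcomes". The next sentence is "Statistically significant associations will be further explored". No other criterion for follow-up is given.

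The analysis set for these outcomes is "participants who completed the second appointment only for relationship outcome analyses". Section 3 sets the recruitment target ("We aim to recruit 50 adults receiving SUD treatment") and section 2 the allocation ("Participants will be randomly assigned to receive either the disclosure intervention (n=25) or a control intervention", with 25 in the control arm as well). At most 50 people can therefore contribute.

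Section 1 places the outcomes among the secondary, exploratory aims: "relationship characteristics, including social support and enacted stigma, and commitment to sobriety". The primary aims are acceptability, feasibility and decision-making quality. Moderation by opioid use is not among the listed aims.

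The plan states no alpha, no coding of baseline opioid use and no expected retention. It does not promise interaction estimates or confidence intervals.

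**The concern.** An interaction is estimated far less precisely than a main effect, and this trial is small to begin with. If significance alone decides which interactions are pursued, two distortions follow. Those that pass are on average exaggerated, because only large estimates can pass. Those that fail may be taken to show that opioid use does not matter, when the data could not have shown otherwise.

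The pilot is meant to prepare for an efficacy trial, and the moderation question rests on a stated hypothesis about opioid use and interpersonal interactions. An inflated interaction, or a false reassurance, could therefore be carried into the planning of that trial.

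**Working it through.** The plan gives no power or precision figure, so there is nothing of its own to reproduce. The calculation below shows scale only.

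**Inputs from the documents.** 50 participants (section 3); 25 per arm (section 2); second-appointment completers only (section 4); two relationship outcomes named, in a list that is left open (section 1).

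**Assumptions.** Two-sided alpha 0.05; binary opioid use with the same split in both arms; outcome SD of 1; all 50 complete, or 40 complete (20% miss the second appointment).

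**Precision.** Let a and b be the numbers per arm with and without baseline opioid use, and n the number of completers. The interaction is a difference of two arm differences, so

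SE = √(2/a + 2/b), df = n − 4, 95% half-width = t(0.975, df) × SE.

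The half-width is also the smallest estimate that reaches significance. The last column uses the noncentral t distribution.

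| Completers, split | a, b | SE (SD units) | 95% half-width | Interaction for 80% power |
|---|---|---|---|---|
| 50, 50/50 | 12.5, 12.5 | √(0.16 + 0.16) = 0.566 | 1.14 | 1.62 |
| 40, 30/70 | 6, 14 | √(0.333 + 0.143) = 0.690 | 1.40 | 1.99 |
| 40, 20/80 | 4, 16 | √(0.5 + 0.125) = 0.791 | 1.60 | 2.28 |

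**Power, and overstatement given significance.** Power is from the noncentral t distribution; overstatement is the mean absolute significant estimate divided by the truth, from 2,000,000 simulated draws.

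| True interaction | 50, 50/50 | 40, 30/70 | 40, 20/80 |
|---|---|---|---|
| 0.5 SD | 14%, 2.8 fold | 11%, 3.3 fold | 9%, 3.8 fold |
| 0.8 SD | 28%, 1.8 fold | 20%, 2.2 fold | 17%, 2.4 fold |
| 1.0 SD | 41%, 1.5 fold | 29%, 1.8 fold | 23%, 2.0 fold |

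**Multiplicity.** Across the two named outcomes, the chance of at least one false positive is 1 − 0.95² = 9.75% if the tests are independent, and about 9.1% at a correlation of 0.5.

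**What the sentence does.** These figures show that the test is weak. They do not show that the sentence leads to a wrong result.

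1. The ANOVA is planned without any significance condition. Significance governs only what is examined after it.
2. Nothing in section 4 makes reporting depend on the p-value.
3. Breaking an interaction into its component arm differences only when the interaction test is significant is common practice, and it limits unplanned contrasts.
4. No section uses a moderation result to choose a subgroup, set an effect size or decide whether to proceed to the later trial.

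**The case for a change.** The best case for a change is that it would be cheap and would improve the write-up. A filter with 9% to 41% power for true interactions of 0.5 to 1.0 SD misses most real moderation and exaggerates what it finds, and calling the analysis exploratory does not undo that. In a pilot this small, the estimate with its interval is the useful product, and one sentence and one table would secure it.

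The arithmetic stands, and so does the observation that no commitment to intervals is made. The rest has less force:

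- Section 4 is brief throughout and promises estimates and intervals for no outcome, the primary ones included. The omission reflects a short plan and is not a flaw peculiar to the moderation analysis.
- Low interaction power and inflation after a significance filter are to be expected in a pilot of about 50. Neither is an error of this design.
- Replacing the sentence has a cost. It follows the moderation sentence directly, but its wording can also cover the t-test and chi-square comparisons. A substitute confined to relationship outcomes could remove follow-up of those comparisons.
- A required table of arm differences by opioid-use level presupposes levels that the plan does not define. With three or more levels there is no single interaction contrast, and for a categorical outcome the SD scale does not apply.
- Treating a significant interaction as no evidence at all would go too far. In the three scenarios above, at a true 0.5 SD, the sign is wrong in 1.7%, 3.5% and 5.3% of significant results. The evidence is weak and inflated, but it is still evidence.

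**Conclusion.** No change to the plan follows. The follow-up rule is conventional, does not suppress non-significant interactions, and serves an analysis that the plan calls exploratory and attaches to no decision. Carrying out section 4 as written yields no incorrect result.

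The remaining gap is one of detail, and analysts fill it as a matter of course: fix the coding of baseline opioid use before looking at outcomes, show interaction estimates with their intervals, and avoid reading non-significance as absence of moderation. The intervals would be wide, about ±1.1 to ±1.6 SD, so a reader would see at once how little the data can say.

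That range assumes two-sided alpha 0.05, a binary moderator split between 50/50 and 20/80, and 40 to 50 completers, none of which the documents state. The conclusion does not depend on the exact values. It would be different if the sponsor intended to use the moderation results to select a subgroup or an effect size for the efficacy trial, but nothing in the documents says so.
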